#### **5.4.4 Interim Analysis**

An interim analysis for futility will be conducted by an independent statistician. The purpose of the interim analysis is to help make a decision whether to continue the trial to the planned sample size, or to stop the trial for futility. No increase or decrease to the sample size will be performed, except to stop the trial for futility, therefore no adjustment to type-1 error is indicated. The interim analysis will be based on conditional power analysis when approximately 60 subjects (per group) have completed the study. Only

absolute lesion reduction count and IGA data (2 point reduction, and Clear or Almost Clear (0, 1)) will be analyzed following the same statistical approaches as pre-specified in the Efficacy Analysis section.

Conditional power for differences in proportions will be calculated using a Normal approximation, two-sided alpha of 0.05, assuming future data will follow the current trend. The decision rules and algorithm for interim analysis are shown in Figure 1.

Figure 1  
 Graphical Illustration of Interim Analysis Algorithm  
 N=120 (N=60 per group)

The independent unblinded statistician will receive the interim study data and the randomization information confidentially from the CRO. The independent statistician will then follow the algorithm above and make a recommendation accordingly. This recommendation will be reviewed by designated sponsor’s representatives who will make the final decision as to continue the trial as planned or stop for futility. Upon receiving the recommendation, the sponsor may ask the independent statistician to examine additional data before the final decision is made. All communications between the unblinded statistician and the sponsor’s representatives will be kept confidential and unknown to all personnel involved in the trial (other sponsor’s personnel, CRO, and clinical center personnel). A charter will be written to describe in detail the process and roles related to

this interim analysis. This charter will name the independent statistician to conduct the interim analysis, and the sponsor's designated personnel that will make final decisions.

#### **5.4.5 Safety Analysis**

Adverse events will be categorized by system organ class and Preferred Term from the current version of MedDRA. Treatment-emergent adverse events will be summarized overall and by seriousness, severity, and relationship to treatment using frequencies and percentages. Adverse events will be considered treatment-emergent if the onset date is on or after the first dose of study medication.

Changes from baseline in vital signs and laboratory parameters, and shifts from baseline in laboratory parameters will be summarized by treatment.

Safety summaries will be presented for the double-blind study period. Additional summaries will be presented for the open-label extension study period, based on the treatment received during the double-blind study period.

In addition, all safety data for omiganan treatment whether from the double-blind or open-label extension period of this study will contribute to the overall long-term safety database for omiganan which will be reported according to ICH-E1 and FDA guidance. Subjects who continue into the open-label extension study period will be included in the planned 300 subjects to be exposed for 6 months and 100 subjects exposed for one year based on their duration of omiganan treatment.

#### **5.4.6 Open-Label Extension Summaries (Safety Extension Period: Week 16, 26, 39, and 52)**

Summary statistics for the open-label extension study period will include baseline demographics, disposition, exposure, safety, and efficacy variables.

Efficacy summaries will include:

- The absolute change from baseline to Weeks 26 and 52 in inflammatory lesions (papules and pustules).
- IGA at Weeks 16, 26, 39, and 52: 2 point reduction; Clear or Almost Clear (IGA 0, 1).

Safety summaries will include:

- concomitant medications
- adverse events that were emergent during the open-label extension study period
- vital signs and laboratory tests at Week 52.

All efficacy and safety summaries in the open-label extension study period will be performed by the original double blind randomized treatment group, and overall.

#### 5.4.7 Compliance (Study Product Utilization and Exposure)

The total number of days product was applied during the double-blind study period from the study medication diary will be summarized by treatment. Per day product usage will be estimated for each dispensing interval and overall as the weight of product used divided by the number of days product was applied. The total number of days product was applied and the per day product usage will be summarized by N, mean, standard deviation, median, minimum, and maximum.

### 6.0 Data Handling Conventions

This section contains the data handling conventions that will be used to carry out the statistical analyses.

#### 6.1 Baseline and Follow-Up Visits

Visits and time points (Double-blind period: baseline, interim [Weeks 1, 3, 6 and 9], final visit [Week 12]; Safety extension period: Weeks 16, 26, 39 and Week 52) for all analyses will be as record on the eCRFs , except as noted below. Baseline will be the later of the non-missing values from the Screening and Baseline/Day 1 visits scheduled to occur prior to receiving study medication. Unscheduled visits will not be used in any analyses but will be included on data listings.

If a subject does not complete the Double-Blind Study Period, the final double-blind visit (Week 12) will be reassigned to a scheduled visit based on the relative day ranges in the following table (where Day 1 is the first day of dosing). If a result already exists for the calculated visit or the calculated visit was not a scheduled visit, the next scheduled visit will be assigned.

Study Day Range	Calculated Visit
$2 \leq \text{Study Day} \leq 15$	Week 1
$16 \leq \text{Study Day} \leq 32$	Week 3
$33 \leq \text{Study Day} \leq 53$	Week 6
$54 \leq \text{Study Day} \leq 74$	Week 9
$\text{Study Day} \geq 75$	Week 12

If an Open-Label subject does not complete the study, the final open-label visit (Week 52) will be reassigned to a scheduled visit based on the relative day ranges in the following table. If a result already exists for the calculated visit or the calculated visit was not a scheduled visit, the next scheduled visit will be assigned.

Study Day Range	Calculated Visit
$89 \leq \text{Study Day} \leq 148$	Week 16
$149 \leq \text{Study Day} \leq 228$	Week 26
$229 \leq \text{Study Day} \leq 319$	Week 39
$\text{Study Day} \geq 320$	Week 52

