7.3.2 Study Procedures by Visit

Visits following the Baseline Visit are to occur at the end of Weeks 1, 3, 6, 9, and 12 (Final Double-Blind Visit). However, interim study visits and the Final Week 12 study visit may be conducted (on an individual subject basis) up to 3 days before or after the regularly scheduled study visit. Additional open-label safety extension visits occur at Weeks 16, 26, 39, and the final extension visit at Week 52. An unscheduled visit may occur in the event that the investigator determines that the subject should be seen for safety or any other reasons.

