7.5.3 Clinical Laboratory Testing

Blood samples (approximately 11 mL) will be collected at Screening and the Week 12 Visit (Early Termination, or Final Visit for the double blind study period) and at the open-label safety extension Week 52 Final Visit, for hematology and chemistry laboratory analysis (total expected volume of approximately 35 ml). A central laboratory will perform the sample analysis for all study sites. Instructions for sample collection, preparation, labeling, and shipping will be provided by the laboratory.

All laboratory values that are considered clinically significant will be reported as an adverse event and followed as such. The laboratory tests will include the following parameters:

- Hematology: Complete blood count (CBC), including hemoglobin, hematocrit, red blood cell (RBC), white blood cell (WBC), count with differential, and platelet count.
- Blood Chemistry/Lipids: sodium, potassium chloride, bicarbonate or carbon dioxide, glucose, blood urea nitrogen (BUN), creatinine, calcium, uric acid, total bilirubin, total protein, albumin, aspartate aminotransferase (AST), alanine aminotransferase (ALT), alkaline phosphatase, gamma glutamyl transferase (GGT), total cholesterol, high-density lipoproteins (HDL), low-density lipoproteins (LDL), triglycerides, and lactic dehydrogenase (LDH).

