## 2.0 Study Design

This study will be conducted as a double-blind, multicenter, randomized, vehicle-controlled, parallel group study at approximately 50 centers (whenever possible, about 16 subjects will be enrolled per center), involving 450 subjects with severe subtype 2, papulopustular rosacea. After giving informed consent, each subject will be screened for study eligibility according to specific inclusion/exclusion criteria. Eligible subjects will be randomized to one of two treatment groups in a 1:1 ratio. The treatment arms are either: omiganan (b) topical gel or vehicle once daily.

Omiganan or vehicle will be topically applied once daily to the entire facial area; cheeks, chin, forehead and nose, avoiding contact with the eyes, mouth, and inside the nose.

Following baseline testing and evaluation for acceptance into the study, the subjects will be supervised during the first test drug application on Day 1 to ensure that the study treatment is applied correctly. Thereafter, each subject will apply the study treatment at home (unsupervised) once daily for 12 weeks in the double-blind study period. Subjects will then be asked to consent to continue in the open-label safety extension period for 3 months. In the open-label extension, subjects will apply omiganan (b) topical gel. No concurrent rosacea therapy of any kind, especially over the counter antimicrobial soaps or soapless cleansers, prescription topical and/or systemic antibacterial agents, will be allowed during the course of the study. No changes in topical soaps should occur. Other concurrent therapies will be recorded throughout the study. Subjects will have scheduled office visits at Weeks 1, 3, 6, 9, and 12 (Final Visit). Additional open-label safety extension visits occur at Weeks 16, 26, 39 and the final extension visit at Week 52. An unscheduled visit may occur in the event that the investigator determines that the subject should be seen for safety reasons.

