### 6.4 Unscheduled Data

Unscheduled data will not be used in the analyses, but will be presented in the listings.

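### SAP 6.1 and 6.4 keep unscheduled laboratory and vital-sign values out of the change and shift summaries, with no exception for safety

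*SAP*

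**What the plan says.** The exclusion is stated twice in the SAP. Section 6.1: "Unscheduled visits will not be used in any analyses but will be included on data listings". Section 6.4: "Unscheduled data will not be used in the analyses, but will be presented in the listings". Neither section separates efficacy from safety.

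SAP 2.0 gives the purpose of such visits: "An unscheduled visit may occur in the event that the investigator determines that the subject should be seen for safety reasons". Protocol 7.3.2 is wider: "An unscheduled visit may occur in the event that the investigator determines that the subject should be seen for safety or any other reasons".

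For the double-blind period, SAP 5.4.5 plans the following: "Changes from baseline in vital signs and laboratory parameters, and shifts from baseline in laboratory parameters will be summarized by treatment". For the extension, SAP 5.4.6 summarises laboratory tests and vital signs at Week 52 only.

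Protocol 7.3.1 and 7.5.3 schedule blood tests at Screening, at Week 12 or early termination, and at the final extension visit. Protocol 7.5.2 schedules vital signs at those visits and at Week 6.

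Two other provisions bear on the point. Protocol 7.5.3 says: "All laboratory values that are considered clinically significant will be reported as an adverse event and followed as such". SAP 5.4.5 treats an adverse event as treatment-emergent according to its onset date, without reference to the visit.

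**The concern.** The main reason for an unscheduled visit is that an investigator is worried about a subject. Laboratory or vital-sign values obtained there are among the most informative in a trial with few scheduled measurements. Under SAP 6.1 and 6.4 they are listed but not summarised.

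Suppose a laboratory value is normal at Screening, abnormal at an unscheduled visit midway through the extension, and normal again at Week 52. The shift table will show no shift. The listing will hold the abnormal value. The adverse event table will show it only if the investigator judged it clinically significant.

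Safety is part of the primary objective and long-term safety is the secondary objective (Protocol 6, SAP 4.0). At stake is whether the laboratory and vital-sign summaries show the extremes that were observed, or only the values that fell on scheduled dates.

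**Working it through.** This is mainly a check of text against text. The only arithmetic is the spacing of scheduled measurements.

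**Step 1. Gaps between scheduled measurements.** Inputs from Protocol 7.3.1: Screening up to 30 days before Day 1, a window of 3 days either side for double-blind visits, and 14 days either side for extension visits.

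| Measurement | Interval | Nominal | Longest with windows |
|---|---|---|---|
| Laboratory | Screening to Week 12 | 12 weeks from Day 1 = 84 days | 30 + 84 + 3 = 117 days |
| Laboratory | Week 12 to Week 52 | 40 weeks = 280 days | 280 + 3 + 14 = 297 days |
| Vital signs | Screening to Week 6 | 6 weeks from Day 1 = 42 days | 30 + 42 + 3 = 75 days |
| Vital signs | Week 6 to Week 12 | 6 weeks = 42 days | 42 + 3 + 3 = 48 days |
| Vital signs | Week 12 to Week 52 | 40 weeks = 280 days | 280 + 3 + 14 = 297 days |

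A subject who completes both periods has two scheduled post-dose laboratory tests and three scheduled post-dose vital-sign measurements.

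**Step 2. Which values inside those gaps are kept.** A subject who stops early receives the final-visit procedures (Protocol 7.2.3). SAP 6.1 reassigns that visit by study day and moves it to the next scheduled visit if the calculated one was not scheduled. Days 54 to 74 map to Week 9, where no laboratory test is scheduled, so on the natural reading the laboratory result goes to Week 12. Days 149 to 228 map to Week 26, so the laboratory and vital-sign results go to Week 52. Protocol 7.1 also has remaining extension subjects stop with final-visit procedures once the exposure targets are met. Early-termination values therefore stay in the summaries.

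**Step 3. Which values are dropped.** Values recorded at unscheduled visits remain. SAP 6.1 and 6.4 bar them from analysis, so they cannot enter the summaries in SAP 5.4.5 or 5.4.6.

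**Step 4. What reaches the tables another way.** A laboratory value judged clinically significant becomes an adverse event under Protocol 7.5.3, at whatever visit it is found, and is tabulated by onset date under SAP 5.4.5. The general adverse event definition in Protocol 7.5.6.1 can cover an abnormal vital sign, but no sentence requires it as 7.5.3 does for laboratory values.

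**Step 5. What is left.** Two things are missing from the summaries: the size of any change seen at an unscheduled visit, and abnormalities the investigator did not judge clinically significant.

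**Step 6. Baseline.** SAP 6.1 takes the later non-missing value from the Screening and Baseline/Day 1 visits, but laboratory tests and vital signs are scheduled only at Screening. A repeat before first dose that is recorded as unscheduled would be ignored and the superseded Screening value kept. If the abnormal first value stays as baseline, a later abnormal result can appear as no shift.

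**The case against.** The strongest defence is that clinically important findings are already captured. Laboratory values judged significant must become adverse events; Protocol 7.6.11 also calls for an adverse event record when a subject starts non-prophylactic therapy for a condition not in the medical history; and adverse events are tabulated by onset. This stands. A reader of SAP 6.1 might infer that safety findings from unscheduled visits never reach any safety table, and the documents do not support that.

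It also stands that early-termination values are kept, so it would be wrong to infer that every value inside the gaps is lost. The rule works by visit type, not by reason, and Protocol 7.3.2 allows unscheduled visits for reasons other than safety, so the plan does not select data out because they concern safety. It applies to both arms and no between-arm safety test is planned, so no bias between arms is shown.

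The protocol names only a urine pregnancy test at unscheduled visits (7.5.5) and prescribes no laboratory or vital-sign measurement there. It describes no repeat test between Screening and Day 1, and a repeat entered under the Screening visit would escape the exclusion. The baseline point is therefore conditional on how repeats are recorded. Protocol 5.1 reports no systemic absorption detected in the 21-day maximum-use study, which lowers the expected yield of laboratory signals.

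These arguments do not remove the remainder. The adverse event route depends on investigator judgement, which is made open-label in the extension, and an event term does not give the size of a change. Shift tables are meant to check that judgement, and the plan still collects laboratory data to Week 52.

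**Conclusion.** The concern holds in a limited form. As written, laboratory and vital-sign values from unscheduled visits do not enter the change-from-baseline or laboratory shift summaries and appear only in listings. With scheduled laboratory tests 280 days apart in the extension (up to 297 with windows), a transient change there can leave no trace in those summaries. The consequence is under-description of magnitude and of abnormalities not judged clinically significant.

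The number of subjects affected cannot be derived: the documents give no rate of unscheduled visits and no rate of measurement at them, so any count would rest on an arbitrary assumption. Nor should a reader infer that the long-term safety database omits these data, since SAP 5.4.5 says all omiganan safety data from both periods contribute to it.

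The conclusion assumes that some laboratory or vital-sign values are collected at unscheduled visits, and that the exclusion is applied literally. It is a worthwhile correction to the SAP and does not affect the efficacy conclusions.

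**What to change.** - In SAP 6.1 and 6.4, limit the exclusion of unscheduled data to efficacy analyses and by-visit summaries.
- In SAP 5.4.5 and 5.4.6, add for each period a shift from baseline to the worst post-baseline laboratory value and a summary of the worst post-baseline vital signs. Both should use scheduled, early-termination and unscheduled results.
- Define the laboratory and vital-sign baseline as the last value before first dose, including any repeat.
- State that adverse events are tabulated by onset date whatever visit they are found at. This removes the tension between the wide wording of 6.1 and the onset rule in 5.4.5.

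No new measurement is needed, because the values are already to be listed. The cost is SAP wording and one extra table set per period. The downside is that worst-value shifts will look slightly less favourable than by-visit shifts.

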## 6.2 Missing Data

The primary method of dealing with missing data is multiple imputation (MI) technique. All co-primary and secondary endpoints will be analyzed using MI for missing data. As a sensitivity analysis, Observed Case and Baseline Observation Carried Forward (BOCF) will be utilized for the co-primary endpoints only.

The MI technique will be implemented as follows:

a) 100 imputed datasets will be generated to impute missing data using the below SAS code.

1) For inflammatory lesions

```
Proc MI NIMPUTE=100 SEED=20170531  
MIN = . 0 0 0 0 0 0  
MAX = . . . . . . .  
ROUND = . 1 1 1 1 1 1;  
class sex;  
var sex base w1 w3 w6 w9 w12;  
fcs reg(w1) reg(w3) reg(w6) reg(w9) reg(w12);  
run;
```

2) For IGA

```
Proc MI NIMPUTE=100 SEED=20170531  
MIN = . 0 0 0 0 0  
MAX = . 4 4 4 4 4  
ROUND = . 1 1 1 1 1;  
class sex;  
var sex w1 w3 w6 w9 w12;  
fcs reg(w1) reg(w3) reg(w6) reg(w9) reg(w12);  
run;
```

b) The 100 imputed datasets will each be analyzed separately by the methods described in Section 5.4.2.

1) For inflammatory lesions, individual LS means and associated standard errors as well as estimates and standard errors from the pairwise comparison of treatments from the analysis of each imputation will be combined into single estimates, standard errors, and p-value using PROC MIANALYZE as displayed below.

```
Proc MIANALYZE;  
Modeleffects estimate;  
Stderr stderr;  
run;
```

The p-value for the treatment by center interaction will be based on the average of p-values from each the analyses of each imputation.

- 2) For IGA, estimates of the event rates will be based on the average of rates from each imputation. The CMH test statistic from the analysis of each imputation will be converted to a Normal Z score by taking the square root and adjusting for direction (change to a negative value if Omiganan group is worse than Vehicle). These Z scores (with SE=1) will be combined into a single p-value using PROC MIANALYZE as displayed below:

```
Proc MIANALYZE;  
Model effects estimate;  
Stderr SE;  
run;
```

Similarly, the p-values for the one-sided Fisher's Exact test of each imputation will be converted to a Normal Z score using the inverse normal function. These Z scores (with SE=1) will be combined into a single p-value using the same PROC MIANALYZE code.

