7.2.3 Withdrawal from Study Criteria

Reasons for discontinuation from the study include, but are not limited to, the following:

- Adverse Event
- Pregnancy
- Withdrawal By Subject
- Lost To Follow-Up. The Investigator will try to reach the subject, twice by telephone (document telephone calls) and once by certified letter, before considering the subject lost-to-follow-up. The lost to follow-up discontinuation will be reported on the appropriate eCRF, and a copy of the follow-up letter will be maintained in the Investigator's file.
- Study Terminated By Sponsor
- Physician Decision
- Non-Compliance with Study
- Other

All premature discontinuations from the study must be documented by the Investigator on the eCRF, and if due to an adverse event, on the Adverse Event Case Report page of the eCRF. All subjects should attempt to complete all visits and evaluations.

Subjects not completing the entire study should be fully evaluated (i.e., final double-blind Week 12 visit procedures performed during the double-blind period or the final open label Week 52 visit procedures during the open-label period). All subjects are free to withdraw from participating in this study at any time and for whatever reason, specified or unspecified, and without prejudice to his or her medical care by a physician. Subjects who withdrawal from the study will not be replaced.

CONFIDENTIAL

Version Date: 31 March 2017

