### 5.2 Analysis Populations

The Intent-to-Treat (ITT) analysis population will include all randomized subjects. The ITT population will be the primary population for all efficacy analyses. Subjects will be analyzed based on the randomized treatment group, regardless of the treatment actually received.

The All-Treated analysis population will consist of all subjects receiving at least one application of study medication. All safety analyses will be performed on the all-treated population. Subjects will be analyzed based on the treatment actually received, regardless of the treatment group to which they were randomized.

The Per-Protocol (PP) population will include all subjects in the ITT population who provide Baseline and Week 12 efficacy data for all primary endpoints and complete the 12-week treatment period without any major deviations from the protocol. The subjects to be included in the PP population will be determined by the Sponsor/CRO prior to the unblinding of the study. The PP population will be secondary for the co-primary endpoints only.

The Open-Label Intent-to-Treat (ITT) analysis population will include all randomized subjects who complete the Double-Blind Study Period and continue into the Open-Label Extension. The Open-Label ITT population will be the primary population for all Open-Label Study Period efficacy analyses. Subjects will be analyzed based on the randomized treatment group

as assigned at randomization during the Double-Blind Study Period, regardless of the treatment actually received.

The Open-Label All-Treated analysis population will consist of all subjects receiving at least one application of study medication during the Open-Label Study Period. All safety analyses during the Open-Label Study Period will be performed on the Open-Label all-treated population. Subjects will be analyzed based on the treatment received during the Double-Blind Study Period, regardless of the treatment group to which they were randomized.

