#### **5.4.3 Efficacy Analysis**

The co-primary endpoint of absolute change from baseline in inflammatory lesions will be analyzed using an Analysis of Covariance (ANCOVA) model, with treatment as a main effect, and baseline inflammatory lesions and pooled center as covariates. To investigate consistency of efficacy results across study centers, treatment by center interaction will be tested at 0.1 level of significance, and if significant, it will be further be explored.

The co-primary endpoint of IGA will be tested in the following manner: the 2 point reduction and the Clear or Almost Clear (0, 1) will be tested using the Hochberg procedure as follows: Statistical significance will be concluded if both endpoints are significant at a two-sided 0.05 level, or if either endpoint is significant at a two-sided 0.025. Both IGA endpoints will be analyzed using a Cochran–Mantel–Haenszel (CMH) test with center as the stratification factor. If the overall IGA response rates are less than 10%, a Fisher’s Exact test will be used to corroborate the CMH test. All tests of the co-primary endpoints will be analyzed.

If the co-primary endpoints of absolute lesion reduction and the two IGA endpoints (2 point reduction, and Clear or Almost Clear (0, 1)) are significant, the secondary endpoints will be tested sequentially in the order listed as follows:

- Test first secondary endpoint at 0.05. If not significant, stop; otherwise,
- Test second secondary endpoint at 0.05. If not significant, stop; otherwise,
- Test third secondary endpoint at 0.05 using Hochberg (similar to the primary method). If not both IGA (0,1) and IGA 2 point reduction are significant, stop; otherwise,
- Test fourth secondary endpoint at 0.05 using the Hochberg method.

For all efficacy analyses, small centers may be pooled in order to ensure sufficient cell counts for statistical testing.

Subgroup summaries (e.g. Gender, Age, Race, and Center) of the co-primary endpoints will be performed.

[figure not shown]

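### The primary multiple-imputation code leaves out treatment, so under missing-at-random dropout both co-primary effects are pulled toward zero

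*SAP*

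**What the plan says.** SAP section 6.2 makes multiple imputation the primary method: "All co-primary and secondary endpoints will be analyzed using MI for missing data". It says the 100 completed datasets come from the code it prints. For lesions the variable list is "var sex base w1 w3 w6 w9 w12"; for IGA it is "var sex w1 w3 w6 w9 w12". Sex is the only CLASS variable in each call, each visit is imputed by regression, and there is no BY statement.

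The analysis that follows does contain treatment. Section 5.4.3 specifies an ANCOVA "with treatment as a main effect, and baseline inflammatory lesions and pooled center as covariates" and a centre-stratified CMH test for each IGA endpoint. IGA succeeds under Hochberg if both endpoints reach 0.05, "or if either endpoint is significant at a two-sided 0.025".

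Two other provisions determine how much is imputed. Section 5.2 states: "The Intent-to-Treat (ITT) analysis population will include all randomized subjects", so every missing Week 12 value has to be filled in. On the other side, Protocol section 7.2.3 says "Subjects not completing the entire study should be fully evaluated", and SAP section 6.1 says that for subjects who leave early "the final double-blind visit (Week 12) will be reassigned to a scheduled visit" according to study day.

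**The concern.** The imputation model is poorer than the analysis model, and the missing term is the one being estimated. Treatment can reach an imputed value only through the subject's own observed visits. The clearest case is a subject with no post-baseline visit. The only predictors are sex and, for lesions, the baseline count, so the imputed Week 12 distribution is the same in both arms whatever the true effect. That case needs no assumption about visit correlation.

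At stake are the primary lesion difference, the reported response rates (omiganan too low, vehicle too high) and some avoidable loss of power. The same code feeds all the secondary endpoints. Type I error is not the worry: with no treatment effect a model pooled over arms is correct.

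**Working it through.** **Inputs from SAP section 5.1.** Lesion reduction 13.5 vs 4 (difference 9.5), SD 12; IGA 0/1 17% vs 6%; 225 per arm.

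**Assumed, because the documents do not say.** Dropout 10% or 20%, completely at random with constant hazard over 12 weeks; visit correlation 0.6 or 0.8; 25/50/75/90/100% of the effect present at Weeks 1/3/6/9/12; 2-grade rates 33% vs 15% or 47% vs 25%.

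**The plan's own figures reproduce.**
- Lesions: 2 × (1.960 + 1.645)² × 12² / 9.5² = 41.5, so 42 per arm. The t-test gives power 0.948 at 42 and 0.952 at 43, which matches 43.
- IGA 0/1: exact Fisher power at 225 per arm is 0.951. There is almost no margin over 95%, and section 5.1 states no dropout allowance.

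**Bounding case: no post-baseline data for a fraction d.** The difference becomes effect × (1 − d).
- Lesions: 9.5 × 0.9 = 8.55; 9.5 × 0.8 = 7.60.
- IGA 0/1, pooled rate (17 + 6)/2 = 11.5%. At d = 10%: omiganan 0.9 × 17 + 0.1 × 11.5 = 16.45%, vehicle 0.9 × 6 + 0.1 × 11.5 = 6.55%, difference 9.9 points. At d = 20%: 15.9% vs 7.1%, difference 8.8.

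**Dropout spread over time.** The simulated lesion effect carried into the imputed Week 12 value depends on the last observed visit:

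| Last visit observed | Effect carried (of 9.5) | Share of dropouts |
|---|---|---|
| Baseline | 0 | 1/12 |
| Week 1 | 1.7–2.2 | 2/12 |
| Week 3 | 2.9–3.4 | 3/12 |
| Week 6 | 4.1–4.8 | 3/12 |
| Week 9 | 5.5–6.2 | 3/12 |

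The shares are the gaps between visits. At mid-range, the average effect carried is (0×1 + 1.95×2 + 3.15×3 + 4.45×3 + 5.85×3)/12 = 3.69.
- 10% dropout: 0.9 × 9.5 + 0.1 × 3.69 = 8.92, a loss of 6.1%.
- 20% dropout: 0.8 × 9.5 + 0.2 × 3.69 = 8.34, a loss of 12.2%.

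If every dropout has an exit assessment that fills the next scheduled visit, those leaving after Week 9 have a Week 12 value. Week 12 is then missing for 9/12 of dropouts (7.5% or 15% of subjects). The average carried becomes (1.95×1 + 3.15×2 + 4.45×3 + 5.85×3)/9 = 4.35.
- 7.5% missing: 0.925 × 9.5 + 0.075 × 4.35 = 9.11, a loss of 4.1%.
- 15% missing: 0.85 × 9.5 + 0.15 × 4.35 = 8.73, a loss of 8.1%.

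**Full simulation.** 1,500 trials in each of 16 scenarios, with 20 imputations (the SAP has 100), the SAP's limits and rounding, 25 pooled centres, its Z-score combination and Hochberg. Power loss is against by-arm imputation on the same trials.

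| | 10% dropout | 20% dropout |
|---|---|---|
| *No exit assessments* | | |
| Lesion difference (complete data about 9.4) | 8.8–8.9 | 8.2–8.3 |
| IGA 0/1 difference (complete data about 11 points) | 10.3 | 9.4–9.7 |
| Vehicle IGA 0/1 rate (true 6.0%) | 6.3–6.5% | 6.5–7.1% |
| Power loss, IGA 0/1 alone (points) | 1.7–2.5 | 5.0–7.1 |
| Power loss, Hochberg IGA decision (points) | 0.2–0.9 | 0.8–2.7 |
| *Exit assessment for all dropouts* | | |
| Lesion attenuation | about 4% | 8–9% |
| IGA 0/1 difference (points) | 10.5–10.7 | 10.0–10.3 |
| Power loss, Hochberg IGA decision (points) | 0.1–0.4 | 0.3–1.3 |

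Lesion power was 100% throughout. By-arm imputation returned the lesion difference to 9.4.

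**Second check.** A separate large-sample simulation used correlations of 0.5 and 0.8, growing or plateauing effects, and lesion dropout dependent on the last observed change. With dropout spread over visits, lesion shrinkage was 5.4–8.3% at 10% and 11.1–16.6% at 20%; the IGA 0/1 difference was 10.1 points and 9.0–9.3. Adding treatment brought the lesion difference to within about 0.6% of complete data. Neither simulation ran the SAS procedure itself.

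**The case against.** **The printed code is abbreviated.** It shows no input or output dataset, and the lesion combining step shows one estimate where several quantities are to be combined. A BY line could have been left out too. The limit and rounding lists have 7 and 6 entries, matching the printed variables, which rules out a lost treatment variable but not a lost BY line. This remains conjecture: the SAP says the datasets come from this code, and nothing mentions imputation within arm. If by-arm imputation was intended, it still has to be written down.

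**The effect on the trial decision is small.** This stands. Lesion power is unaffected, IGA 0/1 alone is not the decision rule, and the Hochberg loss is at most 2.7 points, or 1.3 if exit assessments are obtained as the protocol asks. Those figures depend on assumed 2-grade rates.

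**The direction is not guaranteed.** Also true. With an effect that wanes sharply just before Week 12 and high visit correlation, the lesion estimate rose by 3–4%. That setting is contrived, and the planning assumptions do not suggest it.

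**Other analyses would show the gap.** Partly. Observed Case and Per-Protocol analyses do not rely on imputed Week 12 values, but both are subsidiary and cover the co-primaries only. The sequentially tested secondary endpoints have no such check.

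**Pooling might suit a different target.** The SAP defines none. If dropouts are not assumed to keep their own arm's course, attenuation is not necessarily bias. Nothing indicates that pooling was chosen for that reason.

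**Conclusion.** The concern holds. As written, the primary imputation ignores treatment while the primary analysis estimates its effect. If the target is the effect had dropouts followed their own arm's course, and the effect grows or holds to Week 12, both co-primary differences are attenuated. For lesions the loss is roughly 4–6.5% at 10% dropout and 8–13% at 20%, depending on exit assessments. The IGA 0/1 difference is about 0.3–0.7 point short of 11 at 10% dropout and 0.7–1.6 points short at 20%.

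Not all of the IGA shortfall comes from the missing treatment term. Adding treatment as a covariate recovers about 60% of it; the rest comes from rounded linear imputation with common slopes and variance. Dropout rate, visit correlation and effect course are all assumptions. The harm is distorted primary estimates and a modest loss of power in a conservative direction. It should be fixed because the correction is cheap, but it does not threaten the validity of a positive result.

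**What to change.** Before unblinding, revise SAP section 6.2 in one of two ways and state that imputation conditions on randomised arm.

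1. Sort by treatment and add `BY trt;` to both PROC MI calls. The limit and rounding lists stay as printed.
2. Add treatment to CLASS and VAR in both calls, and extend each MIN, MAX and ROUND list by one entry in the matching position.

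Both restore the lesion difference. Neither is perfect for IGA imputed as a rounded linear score. By-arm imputation is within 0.5 point on IGA 0/1 but can overshoot the 2-grade difference by up to 1.2 points at 20% missing, which favours omiganan. The covariate version leaves IGA 0/1 about 0.3–0.6 point short. The choice should be made and recorded while blinded. Ordinal imputation of IGA is a separate, optional refinement.

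The cost is a SAP revision with no new data or design change, plus slightly more imputation noise if models are fitted within arms of about 225.
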